9.3 Secondary Analyses

Secondary endpoints of each THAPCA trial are:

1. Survival at 12 months post cardiac arrest;
2. Change in neurobehavioral function from pre-cardiac arrest baseline to 12 month measurement (VABS II);

For survivors only,

3. Neuropsychological scores at 12 month evaluation;

4. Neurological abnormality scores at 12 month evaluation.

Mortality over time will be quantified and described using standard survival analysis techniques including generation of Kaplan-Meier curves and comparing these curves between treatment arms via the logrank test. Survival at 12 months will also be evaluated as a binary outcome using the chi-square test. We expect that almost all subjects will have vital status available at 12 months.

The overall change in VABS-II from baseline to 12 months will be evaluated using a linear regression model with 12-month VABS-II as the outcome, and assigned treatment as a predictor along with baseline VABS-II score. Because the distributions may be substantially skewed, we will examine significance levels and confidence intervals for the treatment effect achieved with the nonparametric Wilcoxon rank-sum test for consistency with the findings of the parametric approach. The Wilcoxon rank-sum test will be based on ranks assigned to the differenced scores (12 month minus baseline). If outcomes unexpectedly appear to have substantially differing distribution shapes between treatment arms, resampling techniques will be used to test significance of, and estimate magnitude of, differences in median outcome between treatment arms.

Neuropsychological testing results for the Mullen Scales of Early Learning (children ≤ 5 years 8 months) will be measured as continuous outcomes. Comparison between the study groups will employ a two-sample t-test if appropriate, or alternatively, the Wilcoxon rank-sum test if basic normality assumptions are not met. As detailed in Table 3 on page 44, for patients 6 years and older there is a battery of neuropsychological tests, with separate outcome measures for each test. Comparison between groups will be based on ranks and employ the Wilcoxon rank-sum test. Patients who do not meet minimum requirements to be tested will be assigned the lowest rank for a test; patients who are tested but are unable to meet the test's basal requirements will be given the second lowest rank for that test; all other patients will receive a rank based on the actual score achieved for that test.

The neurological abnormality scores will be measured as continuous outcomes for those who complete the exam. Comparison between the study groups will employ a two-sample t-test if appropriate, or alternatively, the Wilcoxon rank-sum test if basic normality assumptions are not met.

Narrative descriptors for each element of the PRCA (Section 6.6.4 on page 43) will also be analyzed by study investigators to characterize patterns of neurological dysfunction in survivors (e.g. specific movement disorders or

cognitive deficits).

9.4 Safety Analyses

Safety endpoints of this study are:

1. All-cause 28 day mortality;
2. Incidence of culture proven infection (blood, urine, respiratory, or other) within 7 days of cardiac arrest;
3. Incidence of arrhythmias within 7 days of cardiac arrest;
4. Blood products required within 7 days of cardiac arrest. Blood products are defined specifically here to include red blood cells, platelets, fresh frozen plasma, and cryoprecipitate.

Differences between the two study arms with respect to these binary outcomes will be evaluated using a separate chi-square test for each of the THAPCA Trials. Appropriate exact tests will be employed in the case of excessively small expected cell sizes. Rate ratios and 95% confidence intervals will also be described. A secondary analysis will employ the Mantel-Haenszel test to quantify the treatment effect adjusted by center, and the Breslow-Day test (which we recognize will have limited power, as the number of subjects within most centers will be quite low) will be used to assess if there is evidence that treatment effect varies across center.

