7.8 Hemodynamic Management

Blood pressure will be monitored by an arterial line. This is the usual standard practice in PICUs for a post arrest pediatric patient who would meet the study entry criteria. Secure central venous access will be required for participation in this study. This is common practice for the majority of post arrest patients in order to be able to safely and reliably administer fluids, inotropic/vasopressor agents, etc.

It would be desirable to describe an explicit hemodynamic management algorithm for subjects enrolled in THAPCA, but this is untenable due to the diversity of the post arrest pediatric patient population, the multiple etiologies of cardiac arrest, and other comorbid conditions that would be

represented in a typical pediatric population. Of note, explicit hemodynamic protocols were not described in the adult and neonatal RCTs, which demonstrated efficacy of hypothermia for cardiac arrest or HIE.

In general, goal blood pressure for each case will be maintained in a range normal for age and optimized for other factors such as coexisting conditions as determined by the clinical care team. The clinical care team will determine the optimal preload, afterload, contractility and heart rate for each case enrolled in THAPCA. Fluids including blood products or diuretics will be administered as needed to optimize preload. Inotropic and/or vasopressor agents will be administered as clinically indicated for contractility and blood pressure augmentation. Optimal heart rate will also be determined by the bedside clinical care team. This includes treatment of cardiac arrhythmias. The effects of hypothermia on hemodynamics in adult and neonatal trials have usually been related to heart rate with little impact on blood pressure.¹¹⁸ Bradycardia is commonly associated with decreased oxygen consumption in hypothermia treated cases.¹¹⁹ In pediatric TBI trials tachycardia was observed in some hypothermia treated patients and responded to fluid administration.³⁴

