9.1 General Analytic Issues

THAPCA will be analyzed according to the intention to treat principle, wherein all subjects randomly assigned to a treatment arm will be counted in that arm regardless of adherence to protocol or possible crossover to the other treatment arm. Therefore, this clinical trial will assess whether an initial strategy of hypothermia leads to different rates of death or poor neurological outcome than an initial strategy of normothermia. As THAPCA consists of two separate clinical trials, the alpha level for analysis of each trial is 0.05. All tests will be two-tailed.

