Bleeding. Bleeding will be monitored by measuring the volume per kg of blood products (red blood cells, platelets, fresh frozen plasma, cryoprecipitate) administered during the first seven days. We will also track the number of surgical interventions for bleeding during the first 7 days. Patients with life threatening bleeding or severe coagulopathies will not be eligible for this trial. Life threatening bleeding during the study will be managed per the clinical care team with rewarming to the normal range. Prior TBI studies did not observe bleeding to be more commonly observed in hypothermic patients compared to normothermic patients.

Alterations of Potassium. Initiation of cooling has been associated with slight reduction in potassium serum concentration measurement. Serum potassium levels will be measured at baseline and then at least every 6 hours during cooling and the rewarming period. Rewarming has been associated with mild increase in potassium serum concentration measurement. Therefore, the clinical team will remove potassium from the IV fluids during rewarming and supplement as needed during this period. Thereafter, the clinical care team will measure potassium based on their normal unit practice.

Multiple organ failure and death. Patients who have had cardiac arrests are at high risk for development of multiple organ failure and death. In our previous cohort study, the mortality rate was nearly 50%. Seizures following cardiac arrest varied between 14-26% for in-hospital and out-of-hospital cases. Blood stream infection was also high in the cohort study.

In summary, for the therapeutic hypothermia group of the THAPCA Trials, we do not expect higher rates of adverse effects to be observed based on findings from neonatal and adult RCTs using therapeutic hypothermia for HIE or cardiac arrest.

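### The blood-product safety endpoint is compared only as yes/no; a comparison of volume per kg should be added beside it

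*Protocol*

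**What the plan says.** Safety endpoint 4 in Protocol 9.4 is "Blood products required within 7 days of cardiac arrest", covering red cells, platelets, plasma and cryoprecipitate. The analysis rule for all four safety endpoints follows: "Differences between the two study arms with respect to these binary outcomes" are to be tested by chi-square, separately in each trial. Exact tests replace it where cells are small. The effect measure is also binary: "Rate ratios and 95% confidence intervals will also be described". Mantel-Haenszel and Breslow-Day analyses by center complete the list. No cut-point is written, so receipt of any product is the natural reading.

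Section 10.4.2 describes how bleeding will be followed. "Bleeding will be monitored by measuring the volume per kg of blood products", over the first seven days, and "We will also track the number of surgical interventions for bleeding during the first 7 days". Section 6.4 records products received and operations for bleeding over the same week.

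Section 7.8 shows that a product need not mean a bleed: "Fluids including blood products or diuretics will be administered as needed to optimize preload".

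No part of section 9 compares volume per kg between arms.

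**The concern.** Section 2.3.3 names bleeding among the possible adverse effects of hypothermia, so readers will look to this endpoint for reassurance. Reduced to yes or no, it counts a child given one small transfusion for preload the same as a child transfused repeatedly for hemorrhage. If cooling makes children who would be transfused anyway need more, the planned test cannot register it. If most control children receive something, there is also little room for the proportion to rise. The quantity that would show such an excess is the one 10.4.2 says is measured.

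**Working it through.** **Inputs from the protocol.** Two-sided testing, and "the alpha level for analysis of each trial is 0.05" (9.1). Allocation is 1:1 (6.1). Planned enrollment is 300 to 350 out-of-hospital and 450 to 600 in-hospital (9.6). Children with baseline VABS-II below 70 stay in the safety analyses (9.2), so full enrollment applies.

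**Inputs assumed.** The protocol gives no transfusion rate, volume or spread. I take 50%, 70% and 90% of children transfused, and log-normal volume per kg in recipients with log-SD 1.0 (0.7 and 1.5 as sensitivity). Children given none score zero.

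**Plan's own figure.** There is none for this endpoint. As a check of method only, Table 4 (80% vs 60%, 80% power, 182 in total) and Table 5 (65% vs 50%, 366) reproduce exactly with the continuity-corrected two-proportion formula.

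**Step 1: increase in amount only.** The chi-square uses only the counts receiving product. If those proportions are equal in the two arms, its null hypothesis is true whatever happens to volume, so it rejects at alpha. Simulation (3,000 runs per cell) gave 4% to 6% throughout. Rank-sum power on volume per kg, log-SD 1.0:

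| Transfused in both arms | N=300, 1.5-fold | N=300, 2-fold | N=450, 1.5-fold | N=450, 2-fold |
|---|---|---|---|---|
| 50% | 14% | 33% | 20% | 46% |
| 70% | 40% | 80% | 53% | 93% |
| 90% | 79% | 99.6% | 92% | 100% |

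For the 2-fold case at N=300, the three rows become 54%, 97% and 100% at log-SD 0.7, and 17%, 49% and 88% at log-SD 1.5.

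**Step 2: room for the proportion to rise.** Per-arm size without continuity correction is n = [1.96·√(2p̄(1−p̄)) + 0.842·√(p₁(1−p₁)+p₂(1−p₂))]² / (p₂−p₁)², where p̄ is the mean of p₁ and p₂. Solving for the smallest increase detectable with 80% power, in percentage points:

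| Control rate | N=300 | N=350 | N=450 | N=600 |
|---|---|---|---|---|
| 50% | 16.0 | 15.0 | 13.3 | 11.5 |
| 70% | 13.8 | 12.8 | 11.5 | 10.0 |
| 90% | 7.8 | 7.5 | 6.8 | 6.0 |

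At a 90% control rate and N=300, 7.8 of the 10 available points are needed. At 95%, even a rise to 100% gives n = (0.433 + 0.183)² / 0.05² ≈ 152 per arm. That just exceeds the 150 available, so no possible increase reaches 80% power.

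**Step 3: where each test does better (N=300, log-SD 1.0).**

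| Change with hypothermia | Chi-square | Rank-sum on volume |
|---|---|---|
| Share 70% to 80%, volume 1.5-fold | 53% | 93% |
| Share 70% to 80%, volume unchanged | 52% | 33% |

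Neither test dominates.

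**Step 4: early deaths.** A child who dies before day 7 has less time to be transfused. Assume 70% transfused in both arms, a true 1.5-fold increase, early deaths of 20% with normothermia and 40% with hypothermia, and uniform truncation of volume. Rank-sum power then falls from about 42% to about 15% at 325 children, and from about 60% to about 20% at 525 (the midpoints of the two enrollment ranges).

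**The case against.** The strongest objection is that volume is not simply the better measure. Step 3 shows the proportion wins when only the share transfused changes. Step 4 shows volume can hide an excess if hypothermia also raises early mortality, which matters when 10.4.2 reports cohort mortality of nearly 50%. Product given for preload adds to volume as well as to the yes/no count. All of this stands. A reader might infer from Step 1 that volume should become the main bleeding analysis and the proportion be demoted; these results do not support that.

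It is also fair that 9.4 and 10.4.2 do not strictly contradict each other. The endpoint is product use, and 10.4.2 describes monitoring for risk. A reader might infer that a null chi-square would by itself wrongly establish that there was no excess bleeding. The protocol does not support that either. Operations for bleeding are recorded (6.4), bleeding is a listed expected adverse event (11.2.1), and the DSMB reviews all adverse events (11.2.5).

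Finally, a supplementary safety comparison could sit in an analysis plan that is not at hand. But 9.4 does not leave the form open: it fixes a binary comparison for this endpoint, while the protocol elsewhere names the quantity it intends to measure.

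**Conclusion.** The point holds as a modest, inexpensive improvement. As written, the only planned between-arm comparison of blood products has no power beyond alpha against an increase confined to amount, and loses room as the control rate nears 100%. An excess could be missed; nothing shows that it would be. The first statement follows from the test itself. The rest depends on transfusion rates and volumes the protocol does not give. Under the assumed values, power at N=300 for a doubling of volume ranges from 17% to 100% for the rank-sum test, against about 5% for chi-square. At 50% transfused and a 1.5-fold increase, the added test is also weak (14%). The gap is in the formal comparison, not in bleeding surveillance as a whole.

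**What to change.** In 9.4:

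- State that the binary endpoint is receipt of any listed product, and keep its chi-square and rate ratio.
- Add beside it a Wilcoxon rank-sum comparison by arm of seven-day volume per kg, with zero for children given none. State how the four products are combined, and cross-refer to 10.4.2.
- Show early mortality by arm next to it, with a sensitivity analysis for deaths before day 7, for example volume per day alive.

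The cost is one more safety test on data that 10.4.2 already calls for, using a method 9.3 already applies to outcomes with assigned ranks. The downside is that early death cuts volume short. The sensitivity analysis exposes this but does not fully remove it, which is a further reason to keep the binary comparison.

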9.5 Additional Exploratory Analyses

The primary goal of a randomized trial is to assess treatment effect with respect to various outcomes, and evidence for a treatment effect will be the focus of the primary publications from these trials. Predefined primary and secondary outcomes will be clearly noted as such in relevant reports. However, regardless of the primary study finding, THAPCA will generate a database of uniformly, carefully followed pediatric subjects after cardiac arrest, with details of their post-arrest management. Thus, it will be of interest to use this database to perform exploratory analyses of the trajectory of recovery (by comparing three month and 12 month VABS-II), or factors associated with outcomes. An example would be post hoc identification of patient characteristics, or patient management strategies, associated with a larger treatment effect. These studies will employ appropriate approaches including linear and logistic regression, Cox proportional hazards regression,

and appropriate variants of the mixed model to summarize outcomes over time. Assigned treatment will be included in these analyses as appropriate. Reports of these analyses will be clearly described as exploratory rather than formal hypothesis testing.

Absolute Effect Size	Power = 70% ($\beta = 0.3$)	Power = 75% ($\beta = 0.25$)	Power = 80% ($\beta = 0.2$)	Power = 85% ($\beta = 0.15$)	Power = 90% ($\beta = 0.1$)
10%	500	558	626	710	822
15%	242	272	302	342	396
20%	148	162	182	204	236
25%	100	110	122	138	158
30%	74	82	90	100	116

Table 5: Sample Size Needed (Total) to Detect Various Treatment Effects, Assuming Event Rate in Normothermia Arm of 65% (In Hospital), Two-Sided Test with $\alpha=0.05$

Absolute Effect Size	Power = 70% ($\beta = 0.3$)	Power = 75% ($\beta = 0.25$)	Power = 80% ($\beta = 0.2$)	Power = 85% ($\beta = 0.15$)	Power = 90% ($\beta = 0.1$)
5%	2392	2680	3020	3442	4016
10%	630	704	790	898	1044
15%	294	326	366	414	480
20%	170	188	210	238	274
25%	112	124	138	156	178
30%	80	88	98	110	126

9.7 Interim Analyses and Stopping Rules

This study will be monitored by the Data Safety Monitoring Board (DSMB) appointed by the funding institute (National Institutes of Health). The DSMB will have final jurisdiction regarding frequency of meetings, and appropriate formal monitoring boundaries for study stopping in terms of superiority. In this application, we present what we believe is an appropriate interim analysis plan. A detailed version of this plan will be submitted to the DSMB for approval and possible modification prior to the beginning of study enrollment.

Interim monitoring for superiority of one treatment approach over the other will clearly be appropriate in this study. While many investigators might expect hypothermia to be superior to normothermia, we believe that symmetric monitoring boundaries are appropriate as one cannot rule out a detrimental relative effect of either strategy.

Numerous clinical trials have found early treatment differences that diminished or even reversed as more subjects were enrolled. In a multicenter clinical trial, it is not unusual for early recruitment to be confined to a subset of centers that receive early IRB approval or have a smoother run-

in phase; the experience at these centers may differ from others. Also, a “learning curve” in delivering the study therapies, at some or all centers, is not inconceivable and has been specifically noted for therapies such as hypothermia.¹²⁰ Because of these issues, we strongly recommend monitoring boundaries that are conservative at the early looks at the data; we believe that O’Brien-Fleming-type boundaries,¹²¹ implemented using the Lan-deMets flexible alpha spending function approach,¹²² are appropriate for this study setting.

As this is an expensive study to conduct, early stopping of either or both of the THAPCA Trials for futility (low chance that a treatment effect is found if the trial continues) is a consideration. A conditional power approach, wherein the chance of the study finding a treatment effect (given the data accrued thus far in the study) under various assumed true scenarios is assessed, may be appropriate for the DSMB to address futility issues if this becomes necessary.¹²³ This approach, which requires careful consideration of what treatment effect scenarios are realistic given the study data themselves, encourages dialogue and discussion among DSMB members.

The projected accrual period in this study is five years. We assume that the DSMB will meet prior to study launch, and then twice per year during patient accrual. While flexible α spending will be used, we assume here for illustration purposes that there will be four meetings at which the DSMB will perform interim analysis, and that 10%, 25%, 50%, and 80% of study data (technically, of total statistical information for the primary outcome) are available at the respective meetings. Thus, in our illustration, there would be four interim analyses, with an additional final analysis of the study data if the study is not terminated early. While there is no doubt that the DSMB will integrate the results of the study in the out-of-hospital and in-hospital cohorts in their decision making, we generate stopping boundaries independently for these separately powered trials, in line with this study’s analytic strategy.

It is helpful to simulate how many subjects will be required, since it is possible that enrollment for one or both trials (in-hospital and out-of-hospital arrests) will be curtailed early, because of evidence of superiority. As indicated in Section 9.6 on page 62, the precise effect size is not known. The discussions of stopping rules and properties below assume that the effect size for the primary analysis has been correctly estimated in the study power calculations. All calculations assume a two-sided $\alpha = 0.05$.

The possibility of stopping early is dependent on total information available at the time of each interim look. These chances of stopping early are identical for the THAPCA-OH and THAPCA-IH Trials, assuming each has

the same power and amount of information at a given look at the data. If the sample size is large enough to enable 90% power, it is more likely that a trial would be stopped early, because more statistical information is available than if the sample size is only large enough to enable 80% power. Table 6 shows the actual monitoring boundaries (expressed in terms of p-values), and expected probability of stopping the study (for benefit) at each look if the true effect size is precisely as postulated in the study power calculations.

It is important to note that sample size adjustments are required to adjust for the interim analyses, although these are so slight as to be nearly negligible. For example, if one of the substudies is designed to have 90% power and 500 subjects are required based on no interim analysis, the required sample size increases to 512 under the meeting schedule discussed above.

It is evident from these simulations that if the treatment effects are at least as large as expected *a priori*, the THAPCA Trials have a substantial chance of stopping early due to superiority, despite the conservative stopping boundaries that are pre-specified for each. Also, it should be noted that some “ α spending” occurs from interim analyses, and if either trial is carried to completion, the final determination of overall significance of the primary endpoint at the $\alpha = 0.05$ level will require using a significance level of 0.0426 for the final analysis.

Table 6: Probability of Early Stopping at Interim Analyses

Analysis	Information	2-sided p value	Probability of Stopping, Power = 80% ($\beta = 0.2$)	Probability of Stopping, Power = 90% ($\beta = 0.1$)
First	10%	≤ 0.000000014	negligible	negligible
Second	25%	≤ 0.000015	0.2%	0.4%
Third	50%	≤ 0.003	16.7%	25.5%
Fourth	80%	≤ 0.0235	44.0%	49.0%
Final	100%	≤ 0.0426	19.2%	15.1%

10 Human Subjects Protection

